There is evidence in the literature to support both operative and non-operative treatment of patients with LC1 or LC2 pelvic fractures. There is conflicting evidence that surgical stabilization decreases acute pain and narcotic requirements, although patients are often counseled to that effect. We propose to prospectively randomize patients with lateral compression type pelvic fractures to non-operative versus operative treatment and track which group has less pain, less need for narcotic pain medications, and who mobilizes with physical therapy faster.

POTENTIAL RISKS

If the patient is randomized to operative treatment, he/she will be exposed to all of the risks associated with surgery under a general anesthetic including but not limited to: prolonged intubation, heart attack, stroke and death. These risks are extremely rare and will be explained to the patient and/or family by the anesthesia team, and a separate anesthesia consent will be obtained. The risks of the surgical procedure are rare but include: infection, wound break down, failure of hardware, and neurologic injury. A separate surgical consent will be provided to go into more detail of the risks of the procedure.

The risk of non-operative treatment is displacement of fracture with possible need for surgical intervention or prolonged protected weight-bearing. This is unlikely but will be monitored closely, as per our standard of care.

While the intake questionnaire and information gathered is of a sensitive nature (income, narcotic use, pain and psychiatric history) and it might cause the patient some discomfort to answer truthfully, all information will be kept confidential and no identifiers will be used in publication.

While every attempt will be made to keep all information confidential and the master link between the patient study number and personal identifiers will be destroyed at the completion of the study, there remains a risk of the potential for the loss/breach of confidentiality. This risk will be minimized by storing all paper questionnaires in a secure, locked location and all electronic data will be password protected.

There may be risks in this study which are not yet known.

POTENTIAL BENEFITS

While there are no direct benefits to patients participating in the study (except for those that may accrue from closer clinical observation as a study patient), participation may help determine the best treatment for lateral compression type pelvic fractures in the future.

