The safety monitor (SM) is responsible for providing medical guidance and overseeing participant safety for the study. The SM participates in determining the course of action necessary to meet safety goals and objectives. This is achieved through the review of Serious Adverse Event reports; resolving safety issues; and interacting with the Principal and Sub-Investigators at each site.

Reportable New Information (RNI)

The following information must be reported to the coordinating center IRB within FIVE (5) business days of the investigator becoming aware of the information (please note that a separate RNI must be completed and submitted for each problem/event/report):

- Information that indicates a new or increased risk. For example:
 - New information (e.g., an interim analysis, safety monitoring report, publication in the literature, sponsor report, or investigator finding) indicates an increase in the frequency or magnitude of a previously known risk, or uncovers a new risk
 - An investigator brochure, package insert, or device labeling is revised to indicate an increase in the frequency or magnitude of a previously known risk, or describe a new risk
 - Withdrawal, restriction, or modification of a marketed approval of a drug, device, or biologic used in the research protocol
 - Protocol violation that harmed subjects or others or that indicates subjects or others might be at increased risk of harm
 - Complaint of a subject that indicates subjects or others might be at increased risk of harm or at risk of a new harm
 - Any changes significantly affecting the conduct of the research
- Any harm experienced by a subject or other individual which in the opinion of the local investigator is unexpected and at least probably related to the Human Research procedures and suggests that the research places subjects or others at a greater risk of harm than was previously known or recognized
 - A harm is “unexpected” when its specificity or severity are inconsistent with risk information previously reviewed and approved by the IRB in terms of nature, severity, frequency, and characteristics of the study population
 - A harm is “at least probably related to the Human Research procedures” if in the opinion of the local investigator, the research procedures more likely than not caused the harm (greater than 50% probability)

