- Non-compliance with the federal regulations governing human research or with the requirements or determinations of the IRB, or an allegation of such non-compliance
- Failure to follow the protocol due to the action or inaction of the investigator or research staff
- Breach of confidentiality
- Change to the protocol taken without prior IRB review to eliminate an apparent immediate hazard to a subject

- Incarceration of a subject in a study not approved by the IRB to involve prisoners
- Complaint of a subject that cannot be resolved by the research team
- Premature suspension or termination of the research by the sponsor or the investigator
- Unanticipated adverse device effect (any serious adverse effect on health or safety or any life-threatening problem or death caused incidence in the investigational plan or application – including a supplementary plan or application – or any other unanticipated serious problem associated with a device that relates to the rights, safety, or welfare of subjects)
- Audit, inspection, or inquiry by a federal agency
- Written reports of study monitors

Serious Adverse Event (SAE)

Serious Adverse Events may be discovered during regularly scheduled visits or through unscheduled participant contacts between visits. SAEs will be managed according to the medical judgment of the treating physician and source documentation will be maintained (e.g. laboratory and/or radiology reports, clinical notes, discharge summaries). The following are the categories considered for a serious adverse event and must be reported to the IRB during the continuing review process:

- Serious, unexpected, not related
 - Is unexpected, in terms of nature, severity, or frequency, given the research procedures that are described in the protocol and informed consent document and the characteristics of the participants eligible for the study
 - e.g. Death not due to study participation
- Serious, expected, related
 - Is related or possibly related to treatment/procedures under study; possibly related means there is a reasonable possibility that the incident, experience, or outcome may have been caused by the study procedures or treatments
- Serious, expected, not related

Study patients who experience an SAE will be followed until resolution of the event and a final report will be submitted to the safety monitor and IRB. Please note that SAE's and RNI's may overlap and a single event may be classified under both conditions.

DATA ANALYSIS

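### A treatment-related death or life-threatening event has no mandatory expedited route to the IRB when the local investigator judges it expected

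*Protocol*

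**What the plan says.** All of this is in the protocol; the SAP does not address safety reporting.

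- **POTENTIAL RISKS** names, for the operative group, the risks of "surgery under a general anesthetic including but not limited to: prolonged intubation, heart attack, stroke and death". On frequency it says only: "These risks are extremely rare and will be explained to the patient and/or family by the anesthesia team".
- **ASSESSMENT OF SAFETY, Serious Adverse Event (SAE)** introduces its list with "The following are the categories considered for a serious adverse event and must be reported to the IRB during the continuing review process". There are three categories: serious, unexpected and unrelated; "Serious, expected, related"; and serious, expected and unrelated. The definition under the second reads "Is related or possibly related to treatment/procedures under study".
- **ASSESSMENT OF SAFETY, Reportable New Information (RNI)** lists what "must be reported to the coordinating center IRB within FIVE (5) business days of the investigator becoming aware of the information". Its item on individual harm sets three joint conditions, in the local investigator's opinion: the harm is unexpected, it is more than 50% likely to be due to the research procedures, and it suggests greater risk than was known. Harm is unexpected when "its specificity or severity are inconsistent with risk information previously reviewed and approved by the IRB", judged on nature, severity, frequency and study population. Another item covers information pointing to a rise in the frequency or magnitude of a known risk, or to a new risk.
- The SAE section adds that one event may be both an SAE and an RNI, and that a final report goes to the safety monitor and the IRB once the event resolves. No deadline is attached.
- The safety monitor reviews SAE reports, with no time limit. The only stated frequency is in **KEY ROLES**: annual, for enrolment numbers and medical compliance.

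**The concern.** Inclusion criterion 6 admits only patients whose surgeon would accept either treatment, so in the randomised arm the allocation decides who is assigned to surgery. A death or life-threatening event attributed to the assigned treatment bears directly on whether randomisation should go on. Yet if that event was foreseeable, the stated default is the slower of the two IRB routes.

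This matters more because the documents contain no planned interim safety analysis and no trial-level stopping rule. The RNI section mentions an interim analysis only as an example of an information source, and STUDY DISCONTINUATION deals only with a participant's own withdrawal. Prompt notice to the IRB and the safety monitor is then the main safeguard.

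**Working it through.** **Step 1. Which route does each event take?** Setting the RNI harm item beside the SAE list:

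| Judged by local investigator | RNI harm item (5 business days) | SAE list (continuing review) |
|---|---|---|
| Expected, related or possibly related | No: not unexpected | Yes |
| Unexpected, more than 50% likely related, suggests greater risk | Yes | No category |
| Unexpected, possibly related (50% or less) | No: fails the 50% test | No category |

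The first row has no mandatory fast route. The third has no clear place in either list, although an investigator might choose to report it as information about a new risk.

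**Step 2. Does the frequency criterion settle expectedness?** It could if a reference rate were given, but none is. For an assumed true rate p, the chance of at least one event among 65 surgical patients is 1 − (1 − p)^65:

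- p = 0.1%: 6%
- p = 0.5%: 28%
- p = 1%: 48%
- p = 2%: 73%

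Depending on which rate counts as known, a single event could be surprising or unremarkable. The text leaves that to the investigator.

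**Step 3. How many patients might be allocated to surgery during the wait?** The protocol gives no figure for this, so there is none to reproduce. Inputs:

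- 130 patients, 65 per arm (DESCRIPTION OF THE STUDY DESIGN), allocated equally (RANDOMIZATION).
- Recruitment of 18 months (PROTOCOL SUMMARY, study duration). The same entry estimates 4 years in total; less 1 year of follow-up, that leaves up to 36 months.
- Continuing-review interval: not stated. Assumed 6 to 12 months, counted from the start of recruitment.
- Uniform accrual, with all 130 randomised.

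Allocations to surgery per month = 65 / recruitment months: 65/18 = 3.61, or 65/36 = 1.81. The maximum exposure is that rate times the interval:

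| Recruitment | 6-month interval | 12-month interval |
|---|---|---|
| 18 months | 21.7 | 43.3 |
| 36 months | 10.8 | 21.7 |

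**Step 4. Mean rather than maximum.** With annual review and 18-month recruitment, accrual stops six months after the first review. For an event time uniform over the 18 months:

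- Events in months 0 to 12: mean wait 6 months, 6 × 3.61 = 21.7 allocations.
- Events in months 12 to 18: mean remaining accrual 3 months, 3 × 3.61 = 10.8 allocations.
- Weighted mean: (12 × 21.7 + 6 × 10.8) / 18 = about 18.

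In the other three combinations the reviews divide recruitment evenly, so the mean is half the maximum: 10.8 (18 months, 6-month interval), 10.8 (36 months, 12-month interval) and 5.4 (36 months, 6-month interval).

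**Step 5. Comparison with a five-business-day rule.** Taking five business days as 7 calendar days and a month as 30.44 days: 3.61 × 7/30.44 = 0.83, or 1.81 × 7/30.44 = 0.42. That is at most about one patient.

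**The case against.** A reader might infer that listing "prolonged intubation, heart attack, stroke and death" as risks makes every such event expected. The text does not say so. Listing a risk settles its nature, but expectedness also turns on frequency and study population. An investigator could reasonably treat one surgical death as unexpected, because the protocol calls these risks extremely rare, and report it within five business days. This part of the objection stands: the route is discretionary, not closed.

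A reader might also infer that such events reach the IRB only at continuing review. The documents offer other paths: dual classification as SAE and RNI, the final report after resolution, written monitor reports (themselves on the five-business-day list), and local IRB requirements that each site must meet. None of them closes the gap. Dual classification is permitted but adds no trigger. The final report has no deadline. A monitor's report counts only once written, and nothing says when the monitor must receive the SAE report. The local requirements are not in the documents, so they can be neither relied on nor called inadequate.

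Nor can it be argued that a single event is barred from the fast route because it cannot statistically prove a raised rate. The RNI section asks whether information indicates, or a harm suggests, greater risk; it does not ask for proof. The difficulty is the missing reference rate.

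Three points on size also stand. The 43 needs annual review and an event at the very start of recruitment, before anyone could have had surgery; after a month-12 review the maximum is 6 × 3.61 = 21.7. All the figures fall if the 130 includes observational patients, which is possible: RECRUITMENT speaks of about 130 participants in a study with both arms, and the SAP pools randomised and non-randomised patients. Finally, both treatments are described as standard of care, so some patients allocated to surgery might have had it anyway.

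**Conclusion.** The gap is real but narrow. The protocol does not require expedited IRB notice of a death or life-threatening event from the assigned treatment when the local investigator judges it expected, and it gives no rate against which to judge. An unexpected but only possibly related event falls between the two lists, and the safety monitor has no deadline for receiving SAE reports. The documents do not support saying that such events must be classed as expected or must wait for continuing review.

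The consequence is at most about 11 to 43 further allocations to surgery, with a mean of about 18 under annual review and 18-month recruitment, against about one under a five-business-day rule. These numbers rest on an assumed interval of 6 to 12 months, recruitment of 18 to 36 months, uniform accrual and all 130 patients randomised 1:1. The gap in the reporting rule does not depend on them. It should be closed because doing so is cheap and bears on participant safety.

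**What to change.** Add one item to the five-business-day list under Reportable New Information: any death or life-threatening event that is related or possibly related to the assigned treatment, in either arm, whether or not it is named under POTENTIAL RISKS. Require the same report to go to the safety monitor by the same deadline. Leave other serious, expected events on the continuing-review route.

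This removes the dependence on an unstated reference rate for the most serious events, covers those that are unexpected but only possibly related, and gives the monitor a deadline for them. It changes reporting only, not patient care. The cost is one protocol amendment and a few extra expedited reports, with no added staff or study procedures.

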Study duration: We will recruit for a year and a half. Patients will be followed for 1 year. We estimate 4 years total.

Primary outcome measure: *Pain* as measured by using the arithmetic mean of the four pain severity items on the patient-reported Brief Pain Inventory assessment (BPI) 2-weeks following the patient's injury.

Secondary outcome measures: *Length of stay* will be determined by recording the admission date versus discharge date for the patient's index hospitalization. *Time to first mobilization (bed to chair)* will be determined using the physical therapy notes during the patient's index hospitalization and is defined as days post-injury and days post-operative treatment (if applicable) to time of first mobilization (bed to chair). *Narcotic use* will be determined by cross-referencing the patient's medical record during the index hospitalization and follow-up clinic appointments with patient-reported usage. *Work productivity and impairment* will be determined using the modified WPAI:SHP questionnaire. *Health related quality of life* will be measured using the VR-12 questionnaire. *Pelvic function* will be measured using the Majeed Pelvic Score.

Statistical analysis: We are interested in estimating the causal effect of operative treatment versus non-operative treatment in lateral compression type pelvic fracture patients. For all our

analyses, we will report estimates of the causal effects, standard errors, and confidence intervals. We will also report the results of tests of null hypothesis of no causal effect.

KEY ROLES

Safety Monitor- [name] will be responsible for overseeing patient safety for the study. [name] will review the enrollment numbers and medical compliance annually for the duration of the study.

Coordinating Center Principle & Sub-Investigators- [name] [name] (PI) and the sub-investigators will be responsible for developing a detailed study protocol, providing oversight on study progress and act to correct deficiencies in the conduct of the study. The PI and sub-investigators will also draft the main publications related to the study, and assist with patient consent.

Site Principle & Sub-Investigators- The site PI and sub-investigators will be responsible for oversight on local study progress. The site PI and sub-investigators will also contribute to the main publications related to the study, and assist with patient consent.

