Our primary hypothesis is that the operative treatment group will have lower VAS pain scores compared to the non-operative treatment group both during their hospital stay and in the short-term outpatient follow-up.

Based on the results of a pilot study, we expect pain scores in the non-operative group to have a mean of 5.7 and a standard deviation of 2.3. Assuming a 20% reduction in pain scores, 130 patients (65 per arm) are required to have an 80% chance of detecting, as significant at the 5% level, a decrease in the primary outcome measure from 5.7 in the control group to 4.56 in the experimental group. This is our primary outcome and the study will be powered for this variable.

Primary data analysis will involve direct comparison of the change in value of the reported pain scores at the time points listed below. We will be powered to detect a 20% reduction in pain. Secondary analysis will compare the value of narcotics administered at the distinct time periods. Tertiary analysis will be comparing the time (in days) to mobilization with physical therapy. The previous retrospective pilot study incorporated a propensity factor, generated from well documented sources of pain. As this is a prospectively randomized trial, we do not anticipate needing to accommodate for matching.

RANDOMIZATION

Eligible patients will be randomized in equal proportions to one of the two treatment groups: 1) operative treatment of the lateral compression type fracture, 2) non-operative treatment of the lateral compression type fracture. Allocation will be concealed using a centralized 24-hour computerized randomization system, www.randomize.net, that will allow Internet based allocation. The treatment allocation will be stratified on the following prognostic factors to ensure balance between the intervention groups: 1) patient intubation status at time of enrollment, 2) patient prescription pain medication usage during the month prior to injury.

DATA MANAGEMENT

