APPENDIX B: DATA COLLECTION SCHEDULE

Assessment	Screen / Enroll	Pre-Rand. Base	Post-Rand. Base	96-hour	2 week	6 week	3 month	1 year
Pelvic x-rays	X							
Informed Consent	X							
HIPAA	X							
Stratification Levels (AF03)								
Intubation Status (at time of consent)		X						
Prescription Pain Medication Usage (during month prior to pelvic injury)		X						
Patient Intake (CRF01)								
Demographics (age, gender, race/ethnicity, education)			X					
Smoking History			X					
Previous Injuries			X					
Pre-injury Pain Medication Usage			X					
Pre-injury Work Status (WPAI:SHP)			X					
Pre-Injury Health Status (VR-12)			X					
Pre-Injury Pelvic Function (Majeed Pelvic)			X					
Index Hospitalization - Clinical Intake (CRF02)								
Length of Stay & Discharge Disposition			X					

Assessment	Screen / Enroll	Pre-Rand. Base	Post-Rand. Base	96-hour	2 week	6 week	3 month	1 year
ICU Length of Stay			X					
Date/Time & Mechanism of Injury			X					
Height & Weight			X					
Medical History			X					
Time to Mobilization (Bed to Chair)			X					
Narcotic Use			X					
OR Trip(s) Identification			X					
Classification of All Injuries			X					
Study Injury Characteristics			X					
Study Treatment Characteristics			X					
Patient Follow-Up (CRF03 & CRF04)								
Brief Pain Inventory (BPI)				X	X	X	X	X
Re-hospitalizations or Surgeries					X	X	X	X
Physical Therapy Tracking					X	X	X	X
Post-Injury Pain Medication Usage					X	X	X	X
Post-Injury Work Status (WPAI: SHP)					X	X	X	X
Post-Injury Health Status (VR-12)					X	X	X	X
Post-Injury Pelvic Function (Majeed Pelvic)					X	X	X	X
Clinical Follow-Up (CRF05)								
Ambulation & Weight Bearing Status					X	X	X	X
Pain Medication Usage					X	X	X	X
Fracture Healing Status					X	X	X	X
Complications (type, severity, treatment)					X	X	X	X

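### The protocol's primary hypothesis, outcome and analysis sentence describe different pain comparisons, and the stated 80% power belongs to a comparison of means at one time point, not to a change score

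*Protocol*

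**What the plan says.** These places bear on the primary pain comparison.

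- **Outcome.** The Protocol Summary defines it as BPI pain severity, the mean of the four severity items, 2 weeks after injury. The Primary Endpoint section also names the BPI.
- **Hypothesis.** The Primary Objective and Data Analysis sections name a different instrument and different times. Data Analysis expects that "the operative treatment group will have lower VAS pain scores" than the non-operative group, both in hospital and in short-term outpatient follow-up.
- **Analysis.** Data Analysis states: "Primary data analysis will involve direct comparison of the change in value of the reported pain scores at the time points listed below". No time points follow in that section.
- **Sample size.** The same section says "we expect pain scores in the non-operative group to have a mean of 5.7 and a standard deviation of 2.3". It plans 65 patients in each arm for 80% power at the 5% level, and the effect to be found is "a decrease in the primary outcome measure from 5.7 in the control group to 4.56 in the experimental group".
- **Schedule.** Appendix B marks the BPI at 96 hours, 2 weeks, 6 weeks, 3 months and 1 year. It marks no BPI in the pre- or post-randomisation baseline column, and has no VAS row. Inclusion criterion 7 allows randomisation up to 96 hours after injury.
- **SAP.** The Statistical Analysis section makes the primary analysis for pain a Bayesian hierarchical model of average pain over the first 12 weeks.

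**The concern.** A primary analysis should be identifiable by its instrument, its time point and its summary measure. Here the protocol gives two answers on each: VAS or BPI; 2 weeks, or hospital stay plus short-term follow-up; a score at one time, or a change.

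Three things are at stake.

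- Someone who follows the change sentence literally needs a starting score. The only BPI scheduled before 2 weeks is the one at 96 hours, when the patient may already have been randomised and treated.
- The sample size was worked out for a particular comparison. If another one is primary, its power is not the power stated.
- Several candidates for the primary result leave room to choose among them after the data are seen. The SAP, dated December 2020 and written with results in hand, adds one more.

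**Working it through.** **1. Reproduce the stated sample size.** Inputs from the protocol's Data Analysis section: means 5.7 and 4.56, so a difference of 5.7 − 4.56 = 1.14 (20% of 5.7); SD 2.3; 5% level; 80% power; equal allocation. Sidedness is not stated, so two-sided is assumed.

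n per arm = 2 × (1.96 + 0.842)² × SD² ÷ difference² = 2 × 7.85 × 5.29 ÷ 1.2996 = 63.9, so 64.

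The t-test version gives 64.9, so 65 per arm and 130 in total, as stated. A one-sided test would need 51 per arm, which does not match.

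Power at 65 per arm: the standard error is 2.3 × √(2/65) = 0.403, and 1.14 ÷ 0.403 = 2.83. Then Φ(2.83 − 1.96) is about 80.7% (t-test 80.1%). The calculation is therefore a two-sided comparison of mean scores at one time point.

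**2. Carry it to a change score.** With the same SD at both times and correlation ρ between them, the SD of the change is 2.3 × √(2(1 − ρ)). The documents give no ρ, so a range is shown. Equal SDs and a full 1.14 difference in change are also assumptions. Normal approximation, two-sided 5%:

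| ρ | SD of change | Power, 65 per arm | n per arm for 80% |
|---|---|---|---|
| 0 | 3.25 | 51.5% | 128 |
| 0.2 | 2.91 | 60.8% | 103 |
| 0.3 | 2.72 | 66.6% | 90 |
| 0.4 | 2.52 | 73.2% | 77 |
| 0.5 | 2.30 | 80.7% | 64 |
| 0.6 | 2.06 | 88.5% | 52 |
| 0.7 | 1.78 | 95.4% | 39 |

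At ρ = 0.5 the SD of change equals the SD of the score, so the stated figure carries over. Below 0.5 it is too high, and above 0.5 too low.

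**3. Look at the starting score.** For any change analysis:

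contrast in change = (arm difference at 2 weeks) − (arm difference at 96 hours).

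With a pre-randomisation score the second term is zero in expectation. With the 96-hour BPI it need not be. Early relief in the operative arm would shrink the contrast, and early post-operative pain would enlarge it. The documents do not say when surgery falls relative to 96 hours, or how large any early difference is, so no figure is attached to this step.

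**4. Compare with the SAP.** A 12-week average is a mean of scores over several visits. It is not a change, and it is not the 2-week score.

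**The case against.** The strongest reply is that *change* is only loose wording. The protocol uses similar words for differences between arms: the sample-size sentence calls the step from 5.7 to 4.56 a decrease, and the Primary Objective speaks of a decrease in one group compared with the other. No baseline pain score is named anywhere, and that objective is to compare 2-week assessments. On this reading the sentence means the difference between arms at each visit. The reading is reasonable, but it is not secure. In the same paragraph narcotics are compared by value and mobilisation by days, and only pain is given as a change. The reading also leaves the VAS wording and the missing time points unexplained.

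A reader might go further than the documents allow in four ways.

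- *The primary analysis cannot be run.* It can. The 2-week BPI comparison is available, and so is a change from 96 hours, though its starting score is poor. What the schedule does not supply is a VAS comparison or a change from a pre-randomisation score. Nor does any sentence specify change in VAS: the hypothesis concerns VAS levels, and the analysis sentence names no instrument.
- *The stated power is wrong.* It is tied to the primary outcome measure and it reproduces for that outcome.
- *No VAS is collected.* The schedule shows none, but the case report forms were not supplied, and the Clinical Evaluation section lists an unspecified pain assessment.
- *A change analysis must lose power.* The direction depends on an unknown correlation, and step 3 can act either way.

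It is also fair to say that the SAP does not use a change score, so the power range describes the protocol's sentence and not the analysis the SAP reports.

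**Conclusion.** The point holds as an inconsistency that needs reconciling. The hypothesis, the defined outcome and the analysis sentence do not describe one comparison, and the SAP's 12-week average does not restore the 2-week endpoint.

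The 80% power belongs to the single-time comparison of means. That rests on a two-sided test, complete 2-week data, and the pilot SD of 2.3 applying to the BPI four-item mean at 2 weeks; the protocol does not say which instrument or time point the pilot used. For a change score, 65 per arm could give anything from about 52% to about 95% power over correlations 0 to 0.7, under the assumptions in step 2.

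This should be corrected. The defined endpoint and the sample size already agree with each other, so the correction brings the remaining text into line with them.

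**What to change.** - State one primary hypothesis and one primary analysis: the comparison of BPI severity (four-item mean) at 2 weeks between the randomised groups.
- Replace VAS with BPI in the Primary Objective and Data Analysis sections, and delete the reference to change in value.
- List the visits used for the secondary pain comparisons.
- Do not use the 96-hour BPI as a baseline.
- State the instrument and time point behind the pilot mean and SD.
- In the SAP and the report, give the 2-week result as primary and the 12-week average alongside it as an additional analysis.

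The cost is wording plus one analysis of 2-week BPI data already in the schedule; no new data are needed. Because the SAP already reports results, date and explain the clarification, and point to the June 2016 protocol as the source of the 2-week BPI endpoint.

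### The Data Analysis section states a two-period primary hypothesis and a primary comparison at several unlisted time points, contradicting the single 2-week BPI endpoint for which 65 per arm was calculated

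*Protocol*

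**What the plan says.** **One time point.** The Protocol Summary sets the primary objective at 2 weeks after injury. Its primary outcome measure is the mean of the four severity items on the "Brief Pain Inventory assessment (BPI) 2-weeks following" the injury. The Primary Objective section opens with the 2-week comparison. The Protocol Summary also places patient-reported pain up to 1 year under the secondary objective.

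**Two periods.** The hypothesis in the Data Analysis section is lower pain in the operative group "both during their hospital stay and in the short-term outpatient follow-up". The Primary Objective section gives essentially the same hypothesis directly after its 2-week sentence.

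**Several time points.** The analysis sentence in the Data Analysis section reads: "Primary data analysis will involve direct comparison of the change in value of the reported pain scores at the time points listed below". No list follows in that section. Appendix B schedules the BPI at 96 hours, 2 weeks, 6 weeks, 3 months and 1 year.

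**One power calculation.** The sample size is set for an "80% chance of detecting, as significant at the 5% level", a fall from 5.7 to 4.56. Neither document gives a hierarchy, an alpha split or a joint success rule.

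**The SAP.** The section headed Statistical Analysis makes the primary pain analysis an average treatment effect over the first 12 weeks, from a Bayesian hierarchical model. It does not single out the 2-week contrast.

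**The concern.** The section that should fix the primary analysis does not agree with the endpoint it is meant to analyse. An analyst working from the Data Analysis section cannot tell how many primary comparisons there are, or whether a difference in one period is enough. A trial with a clear in-hospital difference and none at 2 weeks, or the reverse, could be called positive or negative depending on which sentence is followed.

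The stated error rate and power belong to one comparison. Two separate tests need a success rule, and each of the two simple rules costs something: requiring both lowers power, and accepting either raises the false-positive rate. The problem is the number of primary comparisons. It would remain whichever pain scale were used, and whether change or raw score were analysed.

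**Working it through.** **Inputs from the Data Analysis section.** Control mean 5.7 and SD 2.3 ("we expect pain scores in the non-operative group to have a mean of 5.7 and a standard deviation of 2.3"); experimental mean 4.56; 65 per arm; 5% level; 80% power. The documents do not state whether the test is one- or two-sided.

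**Assumptions not in the documents.** The same 1.14-point effect and SD 2.3 in both periods, and a correlation r between the two test statistics from 0 to 0.8.

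**1. The plan's own figure.**
- Difference = 5.7 − 4.56 = 1.14.
- Standard error = 2.3 × √(2/65) = 0.403.
- Standardised effect = 1.14 / 0.403 = 2.83.
- The two-sample t-test at two-sided 5% has power 80.1% with 65 per arm, and 79.5% with 64.
- A one-sided 5% t-test would need only 52 per arm.

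The stated size therefore reproduces as exactly one two-sided 5% comparison.

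**2. Two periods, both must be significant.** Each test has marginal power 80.1%, so joint power = P(Z1 > 1.96 and Z2 > 1.96) for a bivariate normal pair. At r = 0 this is 0.801 × 0.801 = 0.64.

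**3. Two periods, either is enough.** False-positive rate = 1 − P(|Z1| < 1.96 and |Z2| < 1.96) under no effect. At r = 0 this is 1 − 0.95² = 9.75%.

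**4. Two periods, one pooled test.** The mean of two occasions has SD 2.3 × √((1 + r)/2). At r = 0.5 this is 1.99, so the standardised effect is 1.14 / (1.99 × √(2/65)) = 3.26 and power is about 90% (normal approximation). The error rate stays at 5%.

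| Rule | r = 0 | r = 0.5 | r = 0.8 |
|---|---|---|---|
| Both required: power | 64% | 69% | 73% |
| Either suffices: false-positive rate | 9.75% | 9.1% | 7.8% |
| One pooled test: power | 98% | 90% | 85% |
| 2-week test alone: power | 80.1% | 80.1% | 80.1% |

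**The case against.** The strongest reply is that the primary endpoint is not really in doubt. The Protocol Summary and the Primary Objective name 2 weeks, and the sample-size paragraph speaks of one primary outcome for which the study is powered. On that definition the 5% level and the 80% power both hold. This stands: the loss arises only if the hypothesis and analysis sentence of the Data Analysis section are followed with separate tests.

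Three further points also stand.
- The hypothesis joins the periods with a word that most naturally means both are required. The error rate is then protected and only power is lost. No sentence says that either period suffices.
- The analysis sentence does not specify separate tests. One pooled or longitudinal test would keep 5% and, on the same assumptions, exceed 80% power.
- The documents give no in-hospital effect or SD and no correlation between periods, so the figures are illustrations over a stated range.

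A reader might also infer that all the BPI visits in Appendix B are co-primary, and so arrive at a much larger false-positive rate. The documents do not support this. The Protocol Summary lists pain up to 1 year as secondary, and the hypothesis stops at short-term outpatient follow-up.

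The reply does not remove the contradiction. The two-period hypothesis appears in two sections, the time points are plural and unlisted, and no rule connects them to the 2-week endpoint. Nor does the SAP settle it, because it adopts a different time frame.

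**Conclusion.** The point holds as an internal contradiction. The protocol has one primary time point in its endpoint definition and two periods, or several unlisted time points, in its Data Analysis section. The SAP adds a third definition, the 12-week average. The sample size matches only a single comparison.

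If the Data Analysis section is followed with separate 5% tests for the two periods, power is about 64% to 73% where both must be significant, or the false-positive rate is about 7.8% to 9.75% where either suffices. Both ranges assume the planned effect and SD in each period and a correlation of 0 to 0.8.

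It would be tempting to say that the trial cannot deliver both its 5% level and its 80% power. The documents do not support that: the 2-week definition delivers both, and a single pooled test would keep 5% with power of at least 80% on the same assumptions.

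The sponsor should correct this, because the text leaves open what a positive result is.

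**What to change.** **Protocol, Data Analysis.** Replace the analysis sentence with: The primary analysis is a single two-sided 5% test of the between-arm difference in mean BPI severity at the 2-week visit; BPI at 96 hours, 6 weeks, 3 months and 1 year is secondary and cannot establish the primary claim.

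**Protocol, Primary Objective and Data Analysis.** Limit the primary hypothesis to 2 weeks, and move the in-hospital part to the secondary objectives. For later visits this agrees with the Protocol Summary, which already treats pain up to 1 year as secondary.

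**SAP.** Report the 2-week between-arm contrast as the protocol primary, and label the 12-week average as a change from it. The SAP is dated December 2020 and written in the past tense, so this means stating openly which contrast the protocol had specified.

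**Cost.** Two sentences in the Data Analysis section, one in the Primary Objective, and one reported contrast and a label in the SAP. No new patients or data are needed. The small downside is that a difference at another time can no longer be claimed as the primary result. Keeping both periods as jointly required would instead need a stated success rule and a larger trial: about 84 per arm at correlation 0 or 80 at 0.5 (normal approximation, same effect and SD in each period).
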